5.11.2. Immunogenicity on Safety and Efficacy

Association between ADA response categories and safety events will focus on the following events:

- Hypersensitivity (SMQ: Hypersensitivity [Narrow])
- Anaphylaxis (SMQ: Anaphylaxis [Narrow])

Number (%) of patients with the above mentioned safety events will be summarized by treatment-emergent, treatment-boosted, persistent ADA response status, and neutralizing antibody status during the TEAE period.

Association between ADA and the primary and key secondary efficacy endpoints may be explored and summarized in SAF using individual patient spaghetti plots.

The safety and efficacy analyses mentioned above will be conducted using the following ADA response categories:

- ADA positive patients, that is patients with treatment-emergent or treatment-boosted response
- ADA negative patients, that is patients with pre-existing immunoreactivity or negative in the ADA assay at all time points
- Patients with persistent ADA response

- NAb positive patients, that is patients who were positive in the NAb assay at any time point analyzed.
- Maximum post-baseline titer level in treatment-emergent or treatment-boosted ADA positive patients:
 - High,
 - Moderate,
 - Low

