Positive anti-drug antibody (ADA) was observed in 50 patients (64.9 %) at any time, 31 of which (40.3% out of total) were categorized as persistent treatment-emergent ADA. The rate of occurrence of persistent ADA were similar across cohorts with a trend of higher rates in the adolescents compared with school-going children. Six patients (12.0%) had high titers ( $> 10,000$ ), 4 from the 2 mg/kg groups and 2 from 4 mg/kg groups. Within each age group, there also seemed to be a trend for higher incidence of persistent ADA in lower dose cohorts as compared to higher dose cohorts. Dupilumab concentrations in patients with high titers were markedly reduced compared to those with a negative response, or low or moderate titers. These patients had an inferior clinical response to the study drug as compared to the overall study population. The high titer ADAs were not associated with any systemic symptoms of hypersensitivity in these patients, although one of these patients did experience an injection site reaction, which was mild in intensity.

Standard safety monitoring used in previous trials with dupilumab is planned to be conducted during this study. An internal safety monitoring team will be reviewing blinded data at regular intervals during the study to monitor the safety of patients. An Independent Data Monitoring Committee (IDMC) overseeing the entire dupilumab clinical development will be in place for the duration of the study to monitor the safety of the patients and to provide the sponsor with appropriate recommendations in due time to ensure the safety of the patients.

Additional information can be found in the Investigator's Brochure.

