4.5. Safety Variables

4.5.1. Adverse Events and Serious Adverse Events Variables

Adverse events and serious adverse events will be collected from the time of informed consent signature and then at each visit until the end of the study. All adverse events are to be coded to a “Preferred Term (PT)”, “High Level Term (HLT)” and associated primary “System Organ Class (SOC)” according to the Medical Dictionary for Regulatory Activities (MedDRA, latest version).

An **Adverse Event** is any untoward medical occurrence in a patient administered a study drug which may or may not have a causal relationship with the study drug. Therefore, an AE is any unfavorable and unintended sign (including abnormal laboratory finding), symptom, or disease which is temporally associated with the use of a study drug, whether or not considered related to the study drug.

AEs also include: any worsening (i.e. any clinically significant change in frequency and/or intensity) of a pre-existing condition that is temporally associated with the use of the study drug; abnormal laboratory findings considered by the investigator to be clinically significant; and any untoward medical occurrence.

A **Serious Adverse Event** is any untoward medical occurrence that at any dose results in death; is life-threatening; requires in-patient hospitalization or prolongation of existing hospitalization; results in persistent or significant disability/ incapacity; is a congenital anomaly/ birth defect; or is an important medical event.

The criteria for determining whether an abnormal laboratory, vital sign or ECG finding should be reported as an AE are as follows:

- Test result is associated with accompanying symptoms, and/or
- Test result requires additional diagnostic testing or medical/surgical intervention, and/or
- Test result leads to a change in dosing (outside of protocol-stipulated dose adjustments) or discontinuation from the study, significant additional concomitant drug treatment, or other therapy

The pre-treatment period is defined as the period from the patient providing informed consent up to the first dose of study drug. The treatment and follow-up period is defined as the period from the administration of first study dose to the EOS visit.

The pre-treatment AE and treatment emergent AE (TEAE) are defined as following:

- Pre-treatment signs and symptoms (Pre-treatment AEs) are AEs that developed or worsened in severity during pre-treatment period.

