10.5. Search Criteria for TEAE of Special Interest/TEAE Syndrome¹

AESI	Search Criteria
Anaphylactic reactions	
For SMQ “anaphylactic reaction” An algorithmic approach will be used. A case must include either:
 
 1. A narrow term (a term from Category A); 2. Patient with both a term from Category B AND a term from Category C; 3. Patient with a term from Category D AND { a term from Category B - OR a term from Category C } 
For bullets 2 and 3, the search terms that are included under the SMQ for a particular event need to have the same start date (for e.g. if search shows cough (category B term) occurring at day 3 and urticaria (category C term) occurring at day 7, this event is not adjudicated as anaphylactic reaction as this is inconsistent with the clinical presentation of anaphylaxis as an acute event with simultaneous involvement of 2 or more body systems.
 
Note: manual adjudication of relevant PTs will be required by the study medical monitor, before database lock

Systemic or severe hypersensitivity reactions	
Hypersensitivity: Narrow SMQ for hypersensitivity excluding preferred term equal to dermatitis atopic or eczema
 
For systemic hypersensitivity, events in which 2 or more body systems are involved (as defined by System Organ Class) would be considered for adjudication based on further medical judgement
 
For severe hypersensitivity, an additional search will be done;
 
 - HLT = Injection site reactions and Severity = “severe” - HLT = Allergies to foods, food additives, drugs and other chemicals and Severity = “severe” or Serious=“Yes” 
Note: manual adjudication of relevant PTs will be required by the study medical monitor, before database lock

Malignancy	
 • SMQ “Malignant tumours” • SMQ “Tumours of unspecified malignancy”
Helminthic infections ²	-HLT = Cestode infections

	
-HLT = Helminthic infections NEC
 
-HLT = Nematode infections
 
-HLT = Trematode infection

Suicidal behavior	
Include the following PTs
 
 • Completed suicide • Suicidal ideation • Suicide attempt • Depression suicidal • Suicidal behavior

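### The ADA safety summary in SAP 5.11.2 counts atopic dermatitis terms as hypersensitivity, although SAP 10.5 removes them, and it uses a narrower anaphylaxis definition than 10.5

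*SAP*

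**What the plan says.** SAP 5.11.2 names two safety events for the ADA analysis. One is given as "Hypersensitivity (SMQ: Hypersensitivity [Narrow" and the other as "Anaphylaxis (SMQ: Anaphylaxis [Narrow". Neither line carries a preferred-term exclusion or points to Appendix 10.5. The planned output is descriptive: "Number (%) of patients with the above mentioned safety events will be summarized by treatment-emergent, treatment-boosted, persistent ADA response status", and also by neutralizing antibody status, over the TEAE period. No test is specified and no split by treatment group is mentioned.

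SAP 10.5 sets the search criteria for adverse events of special interest (AESIs). In the row for systemic or severe hypersensitivity reactions, the base search is the "Narrow SMQ for hypersensitivity excluding preferred term equal to dermatitis atopic or eczema". For anaphylactic reactions it uses an algorithm. A Category A (narrow) term qualifies, and so does "Patient with both a term from Category B AND a term from Category C", or a Category D term with a B or C term. The combined terms must share a start date. Manual adjudication by the medical monitor is required before database lock.

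SAP 4.5.1 counts as an adverse event "any worsening (i.e. any clinically significant change in frequency and/or intensity) of a pre-existing condition" that is temporally associated with study drug. It then treats all adverse events collected during treatment and follow-up as TEAEs.

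**The concern.** Every child enters with IGA 4 (protocol 6.2.1), and clinically significant worsening of the disease is a reportable adverse event. Flares coded to dermatitis atopic or eczema stay out of the 10.5 hypersensitivity search but enter the ADA table in 5.11.2. That table then mixes two things: possible immune reactions to the drug, and activity of the disease being treated.

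The mixing need not be neutral with respect to ADA. Protocol 3.2.3 reports that high-titer patients in the earlier pediatric study had markedly reduced drug concentrations, and says of them: "These patients had an inferior clinical response to the study drug as compared to the overall study population". If weaker response leads to more reported flares, loss of efficacy would appear as hypersensitivity. If flares are simply common in both groups, they dilute a genuine association.

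The anaphylaxis mismatch works by omission. A case reaching AESI status through the B-plus-C or D routes would appear in the AESI tables but not in the summary meant to relate anaphylaxis to ADA. Hypersensitivity and anaphylaxis are the only two safety events that 5.11.2 names for this purpose.

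**Working it through.** The plan states no figure on this point, so there is nothing to reproduce. The check is a comparison of the text, followed by an illustration on assumed rates.

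**Comparison of definitions**

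| Event | SAP 5.11.2 | SAP 10.5 |
|---|---|---|
| Hypersensitivity | Narrow SMQ, no exclusion | Narrow SMQ minus dermatitis atopic and eczema; then multi-system, severity and adjudication steps for the AESI |
| Anaphylaxis | Narrow terms only | Category A, or B+C, or D with B or C; then adjudication |

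Nothing carries the exclusion from 10.5 into 5.11.2. That the narrow SMQ contains both terms is an inference: the term list is not in the documents, but excluding the terms would have no purpose otherwise. The chain is then complete. Worsening is an adverse event, on-study adverse events are TEAEs, and 5.11.2 counts TEAEs.

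**Illustration 1: no true association, comparison within dupilumab patients.** Let h be the true hypersensitivity rate (equal in both ADA groups), f the flare-TEAE rate in ADA-negative patients, and k the ratio of flare rates, ADA-positive to ADA-negative. Hypersensitivity and flare are taken as independent.

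- Counted rate, ADA-negative = 1 - (1 - h)(1 - f)
- Counted rate, ADA-positive = 1 - (1 - h)(1 - kf)

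Assumed: h = 2% or 4%; f = 5%, 10% or 15%; k = 1, 1.5 or 2.

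| h | f | ADA-negative | ADA-positive, k=1.5 (RR) | ADA-positive, k=2 (RR) |
|---|---|---|---|---|
| 2% | 5% | 6.9% | 9.4% (1.36) | 11.8% (1.71) |
| 2% | 10% | 11.8% | 16.7% (1.42) | 21.6% (1.83) |
| 2% | 15% | 16.7% | 24.1% (1.44) | 31.4% (1.88) |
| 4% | 5% | 8.8% | 11.2% (1.27) | 13.6% (1.55) |
| 4% | 10% | 13.6% | 18.4% (1.35) | 23.2% (1.71) |
| 4% | 15% | 18.4% | 25.6% (1.39) | 32.8% (1.78) |

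At k = 1 the risk ratio is exactly 1.00, so the full range is 1.00 to 1.88. With the two-term exclusion the flare component drops out and the ratio is 1.00 throughout.

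**Illustration 2: placebo pooled into the ADA-negative group.** The planned 330 patients give 220 on dupilumab and 110 on placebo. Assumed: placebo patients are ADA-negative; h = 3%; flare rate 5-10% in ADA-negative dupilumab patients; k = 1 or 2; placebo flare rate 10-30%; ADA-positive share of dupilumab patients 5-20%. The apparent ratio then runs from 0.46 to 1.76. The low end has a 20% ADA-positive share, flare rate 5%, k = 1 and placebo flare rate 30%:

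- ADA-positive: 1 - 0.97 × 0.95 = 7.9%
- ADA-negative: (176 × 0.0785 + 110 × 0.321) / 286 = 17.2%
- Ratio: 0.46

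**Illustration 3: a true ratio of 3, diluted.** Assume flares at 5-20%, equal in both groups, and true hypersensitivity of 2% versus 6%, or 3% versus 9%. The counted ratio falls to between 1.15 and 1.73. At the low end, (1 - 0.94 × 0.80) / (1 - 0.98 × 0.80) = 0.248 / 0.216 = 1.15.

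**The case against.** The strongest defence is that the two sections serve different purposes. The 10.5 row concerns systemic or severe reactions and adds multi-system, severity and adjudication steps. Section 5.11.2 looks at hypersensitivity in general, and a broader screen there could be deliberate. This stands in part: the two outputs need not be identical. It does not explain keeping the disease terms, and the SAP gives no reason for doing so.

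The second defence is that the consequences are small, and this largely stands. The table is n (%) with no test or decision rule, and protocol 10.5.5 says only that an assessment of ADA impact on safety may be provided. SAP 5.8.1 plans AESI summaries by preferred term and TEAE listings, and SAP 5.10.1 lists peak titers with neutralizing antibody status. A careful reader could therefore trace which terms drove a count. An anaphylaxis case outside the narrow terms would still be visible in the AESI output. Few such cases are likely: protocol 3.2.4.2 reports no systemic hypersensitivity events in the pediatric study.

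A reader might go further and infer that ADA-positive children will flare more, so the table will show a false immune signal. The documents do not support that. The inferior response in protocol 3.2.3 is reported for high titers only: 6 of 50 ADA-positive patients in an open-label study of ages 6 to under 18. Section 5.11.2 already has titer categories. The ADA-negative category is not restricted to dupilumab arms, so pooling placebo could push the bias the other way.

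Nor does the SAP say why 10.5 excludes the two terms. That they describe the disease under study is the evident reason, but it is a reader's inference. Not every worsening counts either, only flares reported as adverse events and coded to those terms.

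**Conclusion.** The inconsistency is real and clear from the text. As written, flares coded to dermatitis atopic or eczema count as hypersensitivity in the ADA table, and an adjudicated anaphylaxis AESI could be missing from it. The hypersensitivity mismatch can dilute a true association or distort it in either direction, and the direction is not established.

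The size is illustrative only, because the documents give no flare, hypersensitivity or ADA rates for this trial. With no true association, the apparent risk ratio is 1.00 to 1.88 within dupilumab patients and 0.46 to 1.76 if placebo is pooled, under the assumptions listed above. No scenario examined favours keeping the two terms. The point is limited to a descriptive safety table: no primary or secondary endpoint changes. Confidence is high in the mismatch of definitions and low in any particular size or sign of bias.

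**What to change.** In SAP 5.11.2:

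1. Define hypersensitivity as the narrow SMQ excluding the preferred terms dermatitis atopic and eczema. Take over only this base line from 10.5, not the multi-system or severity steps of the AESI row.
2. Define anaphylaxis by the 10.5 algorithm after adjudication.
3. Present the table by treatment group, so that placebo patients are not mixed into the ADA-negative comparator.

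If the sponsor wants the broader hypersensitivity screen, 5.11.2 should say so and give the reason.

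The cost is one or two lines of wording plus a by-arm layout. The searches are already defined in 10.5 and no new data are needed. The change should be made before unblinding, because removing disease terms after an ADA imbalance has been seen would look post hoc.

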5.12. Analysis of Biomarker Data

Descriptive statistics for the observed values, change from baseline and percent change from baseline values by treatment and visit will be provided for the following biomarker variables:

- TARC
- total serum IgE
- Serum Immunoglobulin profile (IgG/IgM/IgA, IgG subclasses)
- Lactate dehydrogenase (LDH)

The Wilcoxon signed-rank test will be used to test if the change or percentage change from baseline value is significantly different from zero. P-value will be reported.

Exploratory analyses for the difference between dupilumab groups and placebo on the change from baseline and percent change from baseline values will be performed using a rank-based ANCOVA model with treatment group as a fixed effect, and the relevant baseline values as covariate. Missing value will be imputed by LOCF method for visits between post-baseline to week 16. After week 16, no imputation will be made. P-value for difference from placebo will be provided.

Correlation of baseline TARC (measured value) and IgE (measured value) with the following clinical endpoints will be explored using ANCOVA model. The model includes the below clinical endpoint as the dependent variable and the log₁₀ based transformed baseline biomarker data, treatment group and their interaction as the predictor variables. Model coefficients and P-value will be provided to indicate significance of the correlation/association.

- Percent change from baseline to week 16 in EASI score
- Percent change from baseline to week 16 in weekly average of worst itch scale
- Change from baseline to week 16 in percent BSA
- Percent change from baseline to week 16 in SCORAD

Correlation of baseline TARC (measured value) and IgE (measured value) with the following clinical endpoints will be explored using the logistic model. The model includes the responder/nonresponder of below clinical endpoint as the dependent variable and the log₁₀ based transformed baseline biomarker data, treatment group and their interaction as the predictor variables. Model coefficients and P-value will be provided to indicate significance of the correlation/association.

- IGA 0-1 at week 16
- EASI-75 at week 16
- improvement (reduction) of weekly average of worst itch scale ≥ 4 from baseline to week 16

Association of positivity to at least one antigen-specific IgE with the following clinical endpoints will be explored using CMH test stratified by weight. The risk ratio and p-value will be provided.

- IGA 0-1 at week 16
- EASI-75 at week 16
- improvement (reduction) of weekly average of worst itch scale ≥ 4 from baseline to week 16

Correlation/association will be implemented on the placebo, dupilumab Q2W, dupilumab Q4W and combined dupilumab (dupilumab Q2W and Q4W) groups, respectively.

All above analyses will be performed on the FAS for

- All observed data, regardless if rescue treatment is used or data is collected after study drug withdrawal
- All observed data with censoring after rescue treatment use

The proportion of patients for whom biomarker concentrations “normalize” (shift from above normal to within the normal range) at Week 16 will also be evaluated.

The additional analysis will be performed on the following biomarkers at week 16:

- Serum total IgE
- Serum LDH

Serum total IgE and LDH are established clinical assays; the upper limit of normal (ULN) from the central lab reference range will determine the threshold for normal vs. elevated status.

Summary tables with normal/elevated status for serum total IgE and LDH at baseline and each post-baseline visit (until end-of-study) will be provided by treatment group.

For the biomarkers with at least 5 evaluable patients in both the dupilumab and placebo treatment groups at Week 16, a Cochran-Mantel-Haenszel test will be conducted to compare the proportion of patients achieving normalized status across treatment groups, stratified by randomization strata (baseline weight group and region), for both the main (LOCF) and sensitivity (OC) analysis approaches. The test statistic p-values for the comparison of the dupilumab groups versus placebo and point estimate with 95% confidence interval will be provided. The proportions will be also summarized by treatment group at each assessment visit.

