### 10.5.6. Analysis of Biomarker Data

All exploratory biomarker data analyses will be performed on the FAS and no multiplicity adjustment is planned. Analyses of exploratory measures will be provided in the SAP.

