2.2. Sample Size and Power Considerations

Due to an inadvertent operational error, 68 patients were potentially unblinded. Details about the error and why it may have been unblinding will be described in the clinical study report. An additional approximately 90 patients were added to the study to ensure that the original number of blinded patients for all treatment groups is available for sensitivity analyses that exclude the potentially unblinded patients. This will maintain study balance and power.

Initially it is estimated that with 80 patients per group, at the 2-sided 5% significance level, the study will have a power table shown as below:

	Placebo + TCS (N=80)	Dupilumab 100mg/200mg Q2W + TCS (N=80)			Dupilumab 300mg Q4W + TCS (N=80)		
		Q2W + TCS	Treatment Difference	Power	Q4W + TCS	Treatment Difference	Power
Proportion of patients with IGA score 0 or 1 at week 16 (%)	5%	28%	23%	97%	22%	17%	87%
Proportion of patients with EASI-75 at week 16 (%)	17%	68%	51%	99%	62%	45%	99%

The significance level is set to 2-sided, 0.05 level. At the time the study was designed, there were no data available on the effects of dupilumab in pediatric patients. The assumptions used for the power calculations were estimated based on results from the R668-AD-1224 study (phase 3 combination study with TCS for adult AD patients) and R668-AD-1021 study (a phase 2b dose-ranging study in adults with AD) for patients with IGA=4 at baseline. Based on the result from the R668-AD-1021 study, the efficacy profile for dupilumab 200 mg Q2W was similar to dupilumab 300 mg Q2W. Therefore, the adult efficacy results from dupilumab 300 mg Q2W were used to assume the treatment effect for dupilumab 100mg/200mg Q2W in the study. This was a conservative assumption as it was expected that the effect of dupilumab in children would be greater than that seen in adults. The sample size calculations were done using nQuery (Version 7.0).

[figure not shown]
Adding 90 patients, the total sample size of the study will be up to approximately 330 patients (110 patients per group), or approximately 262 patients (80, 91 and 91 in Q2W, Q4W, and placebo group, respectively) if the potentially unblinded patients are excluded. With the sample size of 330 patients or 262 patients, the power for the co-primary endpoints will be greater than 90%.

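### The within-arm signed-rank test on percentage change in biomarkers leans towards declaring rises, and misses small to moderate falls, when within-child variability is material (minor, exploratory)

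*SAP*

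**What the plan says.** SAP 5.12 lists TARC, total serum IgE, the immunoglobulin profile and LDH. It plans descriptive statistics for observed values, change and percent change. Then: "The Wilcoxon signed-rank test will be used to test if the change or percentage change from baseline value is significantly different from zero". The p-value is to be reported. For this step the SAP gives no transformation, symmetry check or alternative test, and it does not say whether the result on change or on percentage change governs if they disagree.

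Three other statements bear on the point:

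- The comparison with placebo is a separate analysis that "will be performed using a rank-based ANCOVA model with treatment group as a fixed effect" and the baseline value as covariate.
- The models relating baseline TARC and IgE to clinical endpoints use "the log₁₀ based transformed baseline biomarker data, treatment group and their interaction as the predictor variables". The log scale is thus already in use in this section, but not for the signed-rank test.
- Protocol 10.5.6 sets the status: "All exploratory biomarker data analyses will be performed on the FAS and no multiplicity adjustment is planned".

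**The concern.** The signed-rank reference distribution comes from flipping the signs of the observed values at random, which is legitimate only if those values are symmetric about zero. If baseline *b* and follow-up *f* are exchangeable, log(*f*/*b*) is symmetric about zero. Percentage change is (*f* - *b*)/*b* = exp(log ratio) - 1, which is not. A doubling scores +100% and a halving only -50%, so rises collect the larger ranks although the median is zero. The test can then reject because of shape alone, and in one direction.

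Protocol 8.2.5 intends TARC and total IgE as measures of pharmacodynamic effect and TARC as an exploratory marker of efficacy. At stake is the reading of p-values reported arm by arm. A stable placebo-plus-TCS arm could appear to show a significant rise, or a modest true fall there could go unreported.

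**Working it through.** **Plan's own figure.** There is none: neither document gives an error rate, power or variability for the biomarker tests.

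**Inputs.**

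- n = 110 per arm (SAP 2.2).
- Two-sided 0.05. SAP 2.2 says "The significance level is set to 2-sided, 0.05 level" for the study. No level is stated for the biomarker p-values, so this is assumed.
- SD *s* of the natural-log ratio within a child: not in the documents. Assumed range 0.1 to 1.0.
- Between-child log SD: assumed 1.2. It cancels in the ratio, so it affects only the absolute-change results.

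**Why the shape matters.** Moves of one SD up and down on the log scale become:

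| *s* | exp(*s*) - 1 | exp(-*s*) - 1 |
|---|---|---|
| 0.1 | +10.5% | -9.5% |
| 0.5 | +64.9% | -39.3% |
| 1.0 | +171.8% | -63.2% |

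The imbalance is slight at 0.1 and large at 1.0. What drives it is within-child variability of the ratio, not how skewed the marker is across children.

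**Test.** W+ is the sum of ranks of the positive values. Under the null its mean is n(n+1)/4 = 110 × 111/4 = 3052.5. Its variance is n(n+1)(2n+1)/24 = 110 × 111 × 221/24 = 112,433.75, so its SD is 335.3. The test rejects when |W+ - 3052.5|/335.3 > 1.96.

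**No true change.** Baseline and follow-up were simulated as exchangeable log-normal values, 20,000 simulated arms per setting. The nominal rate is 2.5% per side.

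| *s* | False rise | False fall | Total | False rise at n = 80 |
|---|---|---|---|---|
| 0.1 | 4.1% | 1.2% | 5.3% | 4.0% |
| 0.2 | 7.0% | 0.7% | 7.7% | 6.2% |
| 0.3 | 10.8% | 0.4% | 11.2% | 8.6% |
| 0.5 | 21.0% | 0.1% | 21.1% | 15.3% |
| 0.7 | 31.7% | 0.0% | 31.7% | 24.6% |
| 1.0 | 47.7% | 0.0% | 47.7% | 37.1% |

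On the log ratio the total stays near 5% at every *s*. The bias grows with n, so a larger sample does not cure it.

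**True falls**, n = 110, chance of declaring a fall (at least 2,000 simulated arms per setting):

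| Fall | *s* | Percentage change | Log ratio |
|---|---|---|---|
| 10% | 0.3 | 80% | 94% |
| 10% | 0.5 | 17% | 56% |
| 15% | 0.5 | 55% | 91% |
| 15% | 0.7 | 13% | 67% |
| 20% | 0.7 | 38% | 90% |
| 30% | 1.0 | 35% | 95% |
| 50% | 1.0 | 99.5% | 100% |

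For a true 10% fall at *s* = 1.0, the percentage-change test declares a rise 15.2% of the time and a fall 0.4% of the time.

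**Absolute change.** Under exchangeability it also holds about 2.5% per side. That protection depends on exchangeability. Take the log ratio centred at zero with noise SD 0.5, but let the between-child log values at follow-up be 0.8 or 1.2 times those at baseline. The absolute-change test then rejects about 25% or 29% of the time with between-child log SD 1.2, and 17% or 20% with SD 1.0. The log ratio stays near 5%.

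**The case against.** The strongest reply is that little rests on this test. It is exploratory and within-arm, carries no alpha, and no biomarker appears in the hierarchy of SAP 5.7.2. A spurious rise would be printed beside a median near zero, because SAP 5 and 5.12 require medians and quartiles. This stands and sets the severity.

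A reader might infer that the contrast between dupilumab and placebo will be overstated. The documents do not support that. The contrast has its own rank-based ANCOVA, which does not test symmetry about zero. Only an informal side-by-side reading of within-arm p-values is exposed.

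A reader might also infer that the p-values for every listed marker are wrong, citing the log10 transform as proof. That transform covers only baseline TARC and IgE and speaks to spread between children. The bias depends on variability within a child, which the documents do not give for any marker. A marker that is skewed across children but stable within them has almost no problem, and nothing in the documents shows that LDH or the immunoglobulins are affected.

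The test is, strictly, detecting something real. At *s* = 0.5 the mean percentage change under no change is exp(0.5²/2) - 1 = 13%, and the pseudo-median is about +6%. Rejection is therefore not arithmetically false. It is still misleading as evidence that the marker rose, which is how the p-value will be read.

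Finally, baseline follows two weeks of standardised TCS in children selected for severe disease. A continuing TCS effect or regression to the mean could produce falls that offset false rises. In that case the loss of power is what applies.

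**Conclusion.** The point holds in a limited form. The signed-rank test on percentage change is biased towards a rise, and underpowered for small to moderate falls, when a marker varies materially within a child. Total false rejection runs from about 5-6% at an assumed log-ratio SD of 0.1, through 11% at 0.3 and 21% at 0.5, to 48% at 1.0. It is negligible at the bottom of that range and material from about 0.2 to 0.3. Large falls are still found.

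These figures assume log-normal, exchangeable values, about 110 evaluable children per arm and a 0.05 level. Fewer children, for instance after censoring at rescue, would reduce the false-rise rate. The range of SDs is an assumption, so the documents do not show which markers, if any, are seriously affected.

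Severity is minor. The rank-based ANCOVA and all primary and secondary endpoints are unaffected.

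**What to change.** Replace the sentence in SAP 5.12 with wording to this effect:

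> The within-arm Wilcoxon signed-rank test will be applied to the log of the post-baseline value divided by baseline, as the main test. The geometric mean ratio minus 1 will be reported with its confidence interval, back-transformed from the log scale. Percentage change will be summarised by median, Q1 and Q3, without a p-value.

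If the signed-rank test on absolute change is kept, label it supportive, since it holds its level only when baseline and follow-up are exchangeable. This also settles which result governs when the two disagree.

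The cost is one sentence and one derived variable, with no new data. The downside is that percentage change no longer carries a p-value.
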